### **12.3. Adverse Events of Special Interest**

Adverse events of special interest (AESIs) are adverse events associated with the identified and potential risks of exposure to mepolizumab. Details regarding these risks and the methods by which each AESI will be identified are provided in the Program Safety Analysis Plan (PSAP).

AESIs of systemic reactions and local injection site reactions are collected via targeted eCRF within the study. Events captured on the eCRF as systemic reactions will be further categorized as allergic/hypersensitivity reactions or non-allergic reactions. Events with preferred terms such as injection related reaction or administration related reaction will be considered non-allergic reactions. All remaining events will be considered allergic/hypersensitivity reactions. Events considered by the investigator to represent systemic reactions will be required to be assessed against Sampson's diagnostic criteria for anaphylaxis [[Sampson, 2006](#)].

AESIs of opportunistic infections, malignancies, serious CVT events and serious ischemic events will be identified from a list of relevant preferred terms maintained within a project level reference dataset created based on the MedDRA dictionary available at the time of database freeze for this study, further details of how relevant preferred terms are identified are given in the PSAP.

Separate summary tables showing the number and percent of subjects with each type of AESI, broken down by preferred term will be created. Information will be reported as part of the standard AE tables for AESIs of infections, serious infections, neoplasms, cardiac disorders and serious cardiac disorders.

For each type of AESI a profile summary table will be produced containing information which would include, but not be limited to, the number of occurrences of the event, event characteristics, time to onset, intensity, outcome and action taken.

A listing of any subjects with systemic reactions identified by the investigators as meeting the criteria for anaphylaxis as outlined by the 2006 Joint National Institute of Allergy and Infectious Disease/Food Allergy and Anaphylaxis Network Second Symposium on Anaphylaxis [Sampson, 2006] will be provided.

Adverse events experienced on a day of dosing will be summarised and presented by SOC and preferred term.

A listing of all adverse events experienced by subjects who have had at least one investigator defined systemic/local site reaction will be provided.

The following summary tables will be produced:

- Summary of Adverse Events Of Special Interest: Events Meeting the Criteria for Anaphylaxis (On-Treatment)
- Summary of Adverse Events Of Special Interest: Systemic (Allergic/Hypersensitivity and Non-Allergic) Reactions (On-Treatment)
- Summary of Adverse Events Of Special Interest: Systemic (Allergic/Hypersensitivity) Reactions (On-Treatment)
- Summary of Adverse Events Of Special Interest: Systemic (Non-Allergic) Reactions (On-Treatment)
- Summary of adverse events Experienced on Day of Dosing
- Summary of Adverse Events Of Special Interest: Local Injection Site Reactions (On-Treatment)
- Summary of Adverse Events Of Special Interest: Opportunistic Infections (On-Treatment)
- Summary of Adverse Events Of Special Interest: Malignancies (On-Treatment)
- Summary of Adverse Events Of Special Interest: Serious Cardiac, Vascular and Thromboembolic Events (On-Treatment)
- Summary of Adverse Events Of Special Interest: Serious Ischemic Events (On-Treatment)

The following summary profile tables will be produced:

- Summary Profile of Adverse Events Of Special Interest: Events Meeting the Criteria for Anaphylaxis (On-Treatment)
- Summary Profile of Adverse Events Of Special Interest: Systemic (Allergic/Hypersensitivity and non-Allergic) Reactions (On-Treatment)
- Summary Profile of Adverse Events Of Special Interest: Systemic (Allergic/Hypersensitivity) Reactions (On-Treatment)
- Summary Profile of Adverse Events Of Special Interest: Systemic (Non-Allergic) Reactions (On-Treatment)

- Summary Profile of Adverse Events Of Special Interest: Local Injection Site Reactions (On-Treatment)
- Summary Profile of Adverse Events Of Special Interest: Opportunistic Infections (On-Treatment)
- Summary Profile of Adverse Events Of Special Interest: Malignancies (On-Treatment)
- Summary Profile of Adverse Events Of Special Interest: Serious Cardiac, Vascular and Thromboembolic Events (On-Treatment)
- (This summary will report the events falling into the cardiac disorders and vascular disorders SOC, plus additional thromboembolic events from other SOC [e.g., stroke is categorized under the Nervous System SOC] identified by the Safety Review Team)
- Summary Profile of Adverse Events Of Special Interest: Serious Ischemic Events (On-Treatment)

The following listings will be produced:

- Listing of Adverse Events Of Special Interest: Events Meeting the Criteria for Anaphylaxis
- Listing of Adverse Events Of Special Interest: Systemic (Allergic/Hypersensitivity) Reactions
- Listing of Adverse Events Of Special Interest: Systemic (Non-Allergic) Reactions
- Listing of Adverse Events Experienced on Day of Dosing
- Listing of Adverse Events Experienced by Subjects With Investigator Reported Systemic (Allergic/Hypersensitivity and Non-Allergic) Reactions
- Listing of Adverse Events Of Special Interest: Local Injection Site Reactions
- Listing of Adverse Events Experienced by Subjects With Local Injection Site Reactions
- Listing of Adverse Events Of Special Interest: Opportunistic Infections
- Listing of Adverse Events Of Special Interest: Malignancies
- Listing of Adverse Events Of Special Interest: Serious Cardiac, Vascular and Thromboembolic Events
- Listing of Adverse Events Of Special Interest: Serious Ischemic Events

#### **12.4. Deaths and Serious Adverse Events**

The following summary tables will be produced:

- Summary of Serious Adverse Events (pre-treatment, on-treatment and post-treatment)
- Summary of Number of Subjects and Occurrences of Serious Adverse Events by System Organ Class and Preferred Term

- Summary of Serious Adverse Events by drug product (on-treatment)
- Summary of Exposure Adjusted Serious Adverse Events by drug product
- Summary of Fatal Events (any period)
- Summary of all Non-Fatal Serious Adverse Events (on-treatment and post-treatment)

The following listings will be produced:

- Listing of Fatal Adverse Events
- Listing of all Non-Fatal Serious Adverse Events

### **12.5. Adverse Events Leading to Discontinuation of Investigational Product and/or Withdrawal from the Study and Other Significant Adverse Events**

The following summary tables will be produced:

- Summary of Adverse Events Leading to Permanent Discontinuation of Study Drug or Withdrawal from Study (pre-treatment and on/post-treatment)
- Summary of Adverse Events Leading to Interruption of Study Drug (on-treatment)

The following listings will be produced:

- Listing of Adverse Events Leading to Permanent Discontinuation of Study Drug and/or Withdrawal from the Study

### **12.6. Cardiovascular Events of Interest**

The event specific pages in the eCRF will be summarised. Summaries of events which were reported and confirmed (or not) as cardiovascular following adjudication by the trial Clinical Endpoint Committee (CEC) will be summarised.

The following cardiovascular event listings will be produced for both CEC adjudicated events and all investigator reported events. Arrhythmias, pulmonary hypertension, revascularisation and valvulopathy events will not be adjudicated by the CEC so these event listings will only be produced for investigator reported events. Adjudicated investigator reported events that are not considered by the CEC to be cardiovascular in nature will be identified with a footnote in the relevant investigator reported event listings/summaries.

- Arrhythmias (Investigator reported only)
- Congestive Heart Failure
- Cerebrovascular Events/-strokes
- Deep venous Thrombosis/ Pulmonary Embolism
- Myocardial Infarction /Unstable Angina
- Peripheral Arterial Thrombosis Embolism

- Pulmonary Hypertension (Investigator reported only)
- Revascularisation (Investigator reported only)
- Valvulopathy (Investigator reported only)
- Deaths (all cause)

### **12.7. Pregnancies (as applicable)**

Any pregnancy complication or elective termination of a pregnancy for medical reasons will be recorded as an AE or SAE and included in summaries and listings of AEs/SAEs as described above in Section 12.2.

### **12.8. Clinical Laboratory Evaluations**

The actual values and change from baseline values for clinical chemistry and haematology will be summarised, in separate tables. Summaries of the data outside the normal range and the changes from baseline relative to the normal range will also be produced, including ‘any time post-baseline’, which will include laboratory assessments taken at scheduled, unscheduled and Early Withdrawal visits and will report the most extreme value(s). Data from subjects who have values outside the normal range will be listed. The normal ranges will also be included in this listing. Summaries of values of potential clinical concern will be produced. Data from subjects who have values of potential clinical concern will be listed and the ranges of potential clinical concern will be included in this listing.

A trellis display of maximum post-dose liver function test (LFT) versus baseline LFT and a box plot of maximum LFTs will be produced.

### **12.9. Liver Events**

Subjects with emergent hepatobiliary laboratory abnormalities (for example  $ALT \geq 3x$  Upper Limit of Normal) will be summarised and listed.

Liver event information will be summarised and listed for all subjects who report a liver event, to include:

- The information captured on the Liver Event Assessment Form which is used to calculate the Roussel Uclaf Causality Assessment Method (RUCAM) score.
- The size of the biopsy and the recorded outcomes for the liver biopsy.
- The recorded outcomes for the liver imaging assessment.
- All clinical chemistry results for subjects with Liver Event Criteria

Information on alcohol use for subjects who report a liver event will be included in the listing of substance use. Medical conditions reported at the time of the liver event will be included in the listing of medical conditions (see Section 10.3.2).

### 12.10. Vital Signs

Pre-dose systolic blood pressure, diastolic blood pressure and pulse rate including change from baseline on all visits will be summarised and listed.

### 12.11. 12-lead ECG

Actual and change from baseline (for post-baseline timepoints) values for QTc(F), QTc(B) and heart rate will be summarised by visit. ECG results will also be listed. Abnormal findings and interpretations will be listed separately.

Individual maximum QTc(F) and QTc(B) values will also be summarised to show the number of subjects with maximum values (msec) in the following categories:

- $\leq 450$
- $450 < \text{to} \leq 480$
- $480 < \text{to} \leq 500$
- $> 500$

Additionally, individual maximum changes from baseline in QTc(F) and QTc(B) values will be summarised to show the number of subjects with maximum changes (msec) in the following categories:

- $< -60$
- $\geq -60 \text{ to} < -30$
- $\geq -30 \text{ to} < 0$
- $\geq 0 \text{ to} < 30$
- $\geq 30 \text{ to} < 60$
- $\geq 60$ .

### 12.12. Immunogenicity

Two types of antibody assay will be performed, i.e. an immunogenicity status anti-drug antibody (ADA) assay and neutralising antibody (NAb) assay. For the ADA assay, a screening assessment will be performed which produces a result of positive or negative. For samples with a positive screening result, a confirmation assay will be carried out, which also produces a result of positive or negative. For samples with a positive confirmation result, a titre value will also be obtained to quantify the degree of binding. Subjects will be viewed as positive for the ADA assay if the confirmation assay is positive.

For subjects who have a positive confirmation result for the ADA assay, a neutralising assay will be performed, which again produces a result of positive or negative.

A table will be produced summarising results for the ADA assay in the AT Population by visit. The table will include the number and proportion of subjects in each results category (see below) for each visit. ADA confirmatory assay results will be categorised as follows:

1. Negative
2. Positive

with the table also summarising the minimum, maximum and median titre values collected for subjects with positive ADA confirmatory assays.

Additionally, results for the ADA assay for the AT Population during the first 6 months of treatment within MEA115666 will be summarised by treatment assigned within MEA112997 and visit.

These two tables will also summarise the highest ADA assay confirmatory result obtained for each subject. If a subject had both Negative and Positive confirmatory results, they will be included in the Positive category.

A table will also be produced summarising results for the ADA assay in the AT Population by drug product and visit. For the definitions of the two drug product periods, see Section 9.3.2.1 and Section 9.3.2.2. This table will also summarise the highest ADA assay confirmatory result obtained for each subject whilst receiving each drug product. If a subject had both Negative and Positive confirmatory results, they will be included in the Positive category.

A table will also be produced summarising results for the NAb assay in the AT Population by visit. Neutralising assay results will be categorised as follows:

1. Negative
2. Positive

Additionally, results for the NAb assay for the AT Population during the first 6 months of treatment within MEA115666 will be summarised by treatment assigned within MEA112997 and visit.

These two tables will also summarise the highest neutralising assay confirmatory result obtained for each subject. If a subject had both Negative and Positive results, they will be included in the Positive category.

A table will also be produced summarising results for the NAb assay in the AT Population by drug product and visit. For the definitions of the two drug product periods, see Section 9.3.2.1 and Section 9.3.2.2. This table will also summarise the highest neutralising assay confirmatory result obtained for each subject whilst receiving each drug product. If a subject had both Negative and Positive results, they will be included in the Positive category.

All immunogenicity results (i.e. ADA screening and confirmatory assay results, titre values, NAb results) will be listed.

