8.3.5.3. Immunogenicity Analyses

All immunogenicity endpoints will be summarised using descriptive statistics. The number and percentage of subjects with positive neutralizing antibodies before and after the introduction of the 100mg mepolizumab vial will be tabulated. Further details will be provided in the RAP.

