During the trial the vial strength used when dosing will be changed for most subjects, however this will depend on the timing of regulatory approval. The 100mg dose of mepolizumab will be reconstituted from a vial of 250mg/vial strength up until such time that the 100mg/vial strength is available at the site. Once the 100mg/vial strength is available at the site, all subjects will be dosed with 100mg mepolizumab reconstituted from the 100mg/vial strength at their next treatment visit and for the remainder of the study. This change of vial strength will be when subjects are transitioned onto the new drug product. Hereafter, the 250mg/vial strength will be referred to as mepolizumab drug product 1 (MDP1) and the 100mg/vial strength (to which subjects will transition) will be referred to as mepolizumab drug product 2 (MDP2). In the case that MDP2 is not approved for use by ethics/regulatory at a local site/country subjects will continue to be dosed with MDP1.

Subjects will remain on standard of care asthma therapy, which may be adjusted during the study, at the discretion of their physician. The use of Xolair (omalizumab) or any other monoclonal antibody will not be permitted during the course of the study.

Subjects will be monitored in the clinic approximately every 4 weeks to assess adverse events and asthma status. The Asthma Control Questionnaire-5 (ACQ) will be used to assist the investigator in assessing the subject's asthma status along with spirometry at regular intervals. Exacerbations will also be reviewed at each clinic visit. As some subjects may have previously received placebo while participating in the MEA112997 trial and are naive to mepolizumab, safety lab monitoring will be more frequent at the start of the study. Appropriate safety labs will be drawn prior to starting treatment and then at week 4, 8, 12, 24, 36 and 48. Thereafter, these will be collected every 24 weeks. Labs will also be obtained at 12 weeks after discontinuing mepolizumab. Subjects

discontinuing mepolizumab treatment should be monitored for exacerbation of their asthma.

Serum samples for anti-mepolizumab antibody measurements will be obtained from all subjects at Weeks 0, 4, 24 and 48 of the initial year, week 24 and 48 for every additional year, as well as at the Follow-up Visit. Any anti-mepolizumab antibody positive sample will be tested for neutralising antibody.

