A maximum of two additional anti-mepolizumab antibody samples will be obtained; one immediately prior to the first dose and the other prior to the second dose with MDP2. If the first or second dose coincides with a visit where an immunogenicity sample is already required, it is not necessary to obtain an additional sample.

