**Figure 1 Presentation of Data According to Subject's Former Treatment**

- 2) Change in drug product: Adverse events, immunogenicity and blood eosinophil data will be compared before and after the change in drug product of mepolizumab to investigate whether there is a difference on the safety or efficacy profile following the transition to the new drug product (See [Figure 2](#)).

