### 12.2. Adverse Events

Adverse events will be summarised by preferred term. Numbers will be presented for the whole population. Additionally, events experienced during the first 6 months of treatment within MEA115666 will be presented by treatment assigned within MEA112997.

AEs occurring during pre-treatment, on-treatment and post-treatment phase will be summarised separately.

The number and percentage of subjects experiencing at least one AE of any type, AEs within each body system and AEs within each preferred term will be summarised.

All AEs and SAEs will be summarised by drug product. For the definitions of the two drug product periods, see Section 9.3.2.1 and Section 9.3.2.2.

Exposure adjusted rates of AEs will be presented by drug product to account for any differences in the length of exposure to the two different drug products within the trial. For the definition of exposure adjusted AEs, see Section 9.5.1.

The following summary tables will be produced:

- Overview of all Adverse Events
- Summary of all Adverse Events (on-treatment and post-treatment)
- Summary of drug related Adverse Events (on-treatment)
- Relationship of all Adverse Event SOCs, PTs, and Verbatim Text
- Summary of Most Frequent ( $\geq 3\%$  Incidence prior to rounding) Adverse Events (on-treatment)

- Summary of Number of Subjects and Occurrences of Common On-Treatment Non-Serious Adverse Events by System Organ Class
- Summary of all Adverse Events Experienced During the First 6 Months of Treatment by Treatment Assigned within MEA112997 (on-treatment)
- Summary of all AEs by drug product (on-treatment)
- Summary of Exposure Adjusted AEs by drug product
- Summary of On-Treatment Adverse Events by Highest Anti Drug Antibody Result At Any Time Post Baseline (See Section 12.12 for further details about Immunogenicity)

The following listings will be produced:

- Listing of Subject Numbers for Individual Adverse Events
- Listing of all Adverse Events

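### The highest-result rows of the by-product antibody tables (SAP Tables 7.54 and 7.55) are ever-positive proportions over unequal numbers of samples, so they can differ between vials with no vial effect

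*SAP*

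**What the plan says.** SAP Section 7, item 2, plans to set adverse events, immunogenicity and eosinophils before and after the vial change side by side, "to investigate whether there is a difference on the safety or efficacy profile following the transition to the new drug product". SAP Section 8.3 gives the by-product tabulations the same purpose. Protocol Section 8.3.5.3 adds: "The number and percentage of subjects with positive neutralizing antibodies before and after the introduction of the 100mg mepolizumab vial will be tabulated".

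For ADA, SAP Section 12.12 describes a table by product and visit and then adds: "This table will also summarise the highest ADA assay confirmatory result obtained for each subject whilst receiving each drug product". For NAb it adds: "This table will also summarise the highest neutralising assay confirmatory result obtained for each subject whilst receiving each drug product". Mixed results are resolved upwards: "If a subject had both Negative and Positive confirmatory results, they will be included in the Positive category".

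SAP Section 3 sets the sampling: "obtained from all subjects at Weeks 0, 4, 24 and 48 of the initial year, week 24 and 48 for every additional year", then the Follow-up Visit, plus at most two extra samples at the switch, "one immediately prior to the first dose and the other prior to the second dose with MDP2". Under Sections 9.3.2.1 and 9.3.2.2, a switcher's MDP1 period stops one minute before the first MDP2 dose. The MDP2 period runs to 28 days after the last MDP2 dose. The switch date depends on approval and site supply, treatment has no fixed length, and where MDP2 is not approved subjects stay on MDP1.

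For adverse events, Section 12.2 plans exposure-adjusted rates by product "to account for any differences in the length of exposure to the two different drug products within the trial". Section 12.12 has no counterpart for antibodies. Section 18.1.7 lists Tables 7.56 and 7.57 (ADA and NAb, pre and post change), but Section 12.12 does not describe them. A paired rule (last sample before, first sample after, subjects with both) is written only for eosinophils, in Section 11.5.

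**The concern.** Taking the highest result in a period turns the row into the proportion of subjects ever positive in that period. More samples give more chances to be positive, and the number of samples on each vial is set by logistics and length of stay, not by the vial. Two further features pull the columns apart. Subjects who never switch enter only the MDP1 column. A subject who becomes positive on MDP1 and stays positive is counted again under MDP2.

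Antibody frequency is a secondary endpoint, and Protocol Amendment 2 added samples because of the vial change. The highest-result row is the only summary described in Section 12.12 that covers the whole of each product period, so it is the row a reader is most likely to use to judge the new vial. It could suggest a rise, or hide one, that reflects only sampling.

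**Working it through.** **1. Inputs.** The documents give no antibody rate, switch week, study length or sample size, so there is no figure to reproduce. From the documents: the sampling schedule and the period definitions. Assumed: positivity per sample p of 1%, 2% or 5%, the same on both vials (no vial effect); switch at Week 40, 52 or 76; last dose at Week 96 or 192.

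**2. Samples per period.** The sample before the first MDP2 dose falls in MDP1 and the one before the second in MDP2. The follow-up sample is put in MDP2. Week 0 is left out of MDP1, although Section 9.3.2.1 starts that period on the first dosing day and does not say whether the pre-dose sample counts. Example, switch at Week 40 and last dose at Week 192: MDP1 has Weeks 4, 24 and 40 (3 samples); MDP2 has Weeks 44, 48, 72, 96, 120, 144, 168, 192 and follow-up (9 samples).

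**3. Expected highest-result row, independent samples.** P(ever positive in k samples) = 1 − (1 − p)^k. For p = 2%: 1 − 0.98^3 = 5.9% and 1 − 0.98^9 = 16.6%.

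| Switch week | Last dose week | Samples MDP1 / MDP2 | p = 1% | p = 2% | p = 5% |
|---|---|---|---|---|---|
| 40 | 96 | 3 / 5 | 3.0 / 4.9 | 5.9 / 9.6 | 14.3 / 22.6 |
| 40 | 192 | 3 / 9 | 3.0 / 8.6 | 5.9 / 16.6 | 14.3 / 37.0 |
| 52 | 96 | 4 / 4 | 3.9 / 3.9 | 7.8 / 7.8 | 18.5 / 18.5 |
| 52 | 192 | 4 / 8 | 3.9 / 7.7 | 7.8 / 14.9 | 18.5 / 33.7 |
| 76 | 96 | 5 / 3 | 4.9 / 3.0 | 9.6 / 5.9 | 22.6 / 14.3 |

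The last three columns are the expected percentage ever positive, MDP1 / MDP2. The direction depends on timing, and for some timings the columns agree.

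**4. Correlated samples.** With a beta-binomial model and within-subject correlation ρ, at p = 2% and 3 against 9 samples: ρ = 0.3 gives 4.4 / 8.0; ρ = 0.6 gives 3.3 / 4.6; ρ = 0.9 gives 2.3 / 2.6; ρ near 1 gives 2.0 / 2.0.

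**5. Positivity acquired on treatment and then persistent.** Here MDP2 inherits the MDP1 conversions, so the MDP2 proportion is 1 − (1 − p)^(k1 + k2). At a 2% conversion chance per sample, 4 then 7 samples give 7.8% against 1 − 0.98^11 = 19.9%. Even 3 then 3 give 5.9% against 1 − 0.98^6 = 11.4%.

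**6. Would the adverse-event adjustment solve it?** Take p = 2% per independent sample, a switch at Week 28 and a last dose at Week 168, follow-up sample left out.
- MDP1: Weeks 4, 24 and 28. 1 − 0.98^3 = 5.9% over 28 × 7 + 1 = 197 days (0.54 years), about 10.9 per 100 subject-years.
- MDP2: Weeks 32, 48, 72, 96, 120, 144 and 168. 1 − 0.98^7 = 13.2% over 140 × 7 + 28 = 1,008 days (2.76 years), about 4.8 per 100 subject-years.

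Subject-years alone would show a false fall of about 56% (1 − 4.8/10.9), because sampling is denser early. Dividing first positives by samples tested while still at risk is neutral here. Expected at-risk samples per subject are [1 − (1 − p)^k]/p, that is 0.0588/0.02 = 2.94 and 0.1319/0.02 = 6.59, and both ratios return 2%.

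**The case against.** The strongest reply is about scope. Tables 7.54 and 7.55 are by product and visit, and the highest-result row is one added line. The by-visit rows pool nothing over a period and are not affected. SAP Section 8 requires N and n in summary tables, exposure and attendance by product are tabulated (Tables 7.02 and 5.08), and every antibody result is listed (Listing 7.34). Samples were added at the switch, and pre/post Tables 7.56 and 7.57 are listed; their shells are in separate documents not available here. There are no hypotheses and no tests. The sizes above rest on assumed rates and timings, and they nearly vanish if antibody status is stable within subject.

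Most of this stands, and it rules out three stronger readings that a reader might infer:
- That the planned antibody comparison as a whole cannot separate a vial effect from none. This is not supported, because the by-visit rows and the listed pre/post tables are separate sources.
- That the new vial will look worse. This is not supported, because the direction depends on timing that the documents do not give.
- That there is a high false-positive rate. This is not supported, because no inference is planned whose error rate could be wrong.

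What does not stand is that the gap is already covered. The n at each visit does not tell the reader how many samples lie behind each subject's highest result. Section 12.12 leaves open which samples and subjects enter Tables 7.56 and 7.57. If they copy the eosinophil rule, they may see only the sample about 4 weeks after the first MDP2 dose and miss later conversion.

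**Conclusion.** The point holds for the highest-result rows of Tables 7.54 and 7.55 and no further. Following the stated rule, those rows can differ between products in either direction with no vial effect. At an assumed 2% per independent sample the illustrations run from 5.9% against 16.6% (3 and 9 samples) to 9.6% against 5.9% (5 and 3 samples). The gap closes if sample counts happen to match and positivity does not accumulate, or if status is stable within subject. It remains, even with matched counts, if positivity is acquired on treatment and persists. Rate, persistence, switch week and follow-up are all assumptions, so neither size nor direction can be fixed from the documents. The harm is a misleading descriptive comparison on a question that the SAP says it wants to answer, and it is worth correcting.

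**What to change.** 1. In SAP Section 12.12, define Tables 7.56 and 7.57 as a within-subject comparison in switchers with samples on both sides, using the same number of samples before and after the first MDP2 dose. Showing changes in status (negative to positive, positive to negative) keeps carried-over positives visible.
2. In Tables 7.54 and 7.55, show per product the number of samples tested and the number and percentage positive. Add the number first positive on MDP2 among switchers negative at the sample immediately before the first MDP2 dose, and the number first positive on MDP1 among subjects negative at Week 0. Use at-risk samples tested as the denominator. Subject-years may be shown beside it but not alone, for the reason in step 6 of the working. State whether the Week 0 pre-dose sample belongs to the MDP1 period.
3. If the highest-result row is kept, footnote that it is not a vial comparison because sampling opportunity differs between the periods.

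The cost is SAP wording and programming of four tables; the samples and dates are already collected. Counts of first positives will be small and the rates imprecise. At-risk samples are a neutral denominator only if the chance of a first positive is the same at each sample, whatever the interval since the last one. No version separates vial from time on treatment or drop-out, because MDP1 always comes first, and the text should say so.
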